#### **Number of Patients:**

Approximately 3800 participants will be screened to achieve 1899 randomized for an estimated total of 633 evaluable participants per treatment group (633 in combined placebo arms during Placebo-Controlled period). If there is an assumed 25% discontinuation rate, approximately 1424 patients will complete the Placebo-Controlled period and 1139 will complete the Delayed-Start period (in which the estimated discontinuation rate is 40% over the entire 3 year study).

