### 10. Statistical Considerations

## 10.1. Sample Size Determination

Approximately 1899 patients may be enrolled/randomized in order that 1424 patients complete the Placebo-Controlled period of the study.

The sample size has been calculated to provide 90% power to detect a treatment difference in a functional secondary outcome, that is, change in ADCS-iADL at 78 weeks. Based on estimates of treatment change and standard deviation from the mild ApoE4 carriers (ApoE4 used as a surrogate for amyloid positivity) in pooled solanezumab studies NCT00905372 (H8A-MC-LZAM [LZAM]) and NCT00904683 (Study H8A-MC-LZAN [LZAN]), an expected mean change (SD) in ADCS-iADL score is 2.07 (9.78), which equates to an effect size of 0.212. Using the R package 'pwr' and accompanying function 'power.t.test', 554 completing patients per arm are needed to provide 90% power with  $\alpha$ =0.025. Assuming a 25% dropout rate and a 50% information rate for dropouts, 633 (554/(1-0.25%\*50%)) patients will need to be randomized per arm (633 in combined placebo arms during the Placebo-Controlled period). This equates to a total randomized sample size of 1899.

This calculated sample size provides greater than 90% power to evaluate the primary outcome for the Placebo-Controlled period. Based on estimates of treatment change and standard deviation from the mild ApoE4 carriers in pooled solanezumab studies LZAM/LZAN, an expected mean change (SD) in ADAS-Cog13 score is 2.91 (10.84) which equates to an effect size of 0.269. Using the R package 'pwr' and accompanying function 'power.t.test', 633 patients randomized per arm will provide 99.4% power for this analysis.

Using the three stage hypothesis testing approach to delayed start analysis as outlined in Liu-Siefert and colleagues (2015b), this sample size will provide approximately 80% power for each dose when all patients have the opportunity to complete the 6 month time point at an alpha level of 0.1. At the 18 month time point of the Delayed-Start period, this sample size will provide approximately 50% power.

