#### 10.3.4. Safety Analyses

Safety will be assessed by summarizing and analyzing AEs, laboratory analytes, vital signs, MRI scans, skin and eye examinations, and ECGs during the treatment period.

Safety analyses for the Placebo-Controlled period will include comparisons between LY3314814 dose groups and placebo. All hypotheses will be tested at a 2-sided 0.05 significance level. No adjustments for multiple comparisons will be made.

Safety analyses for the Delayed-Start period will incorporate a "contextualizing cohort" developed through modeling the plausible progression of disease for a placebo treated cohort. Further details on this modeling approach and the analysis methods will be outlined in the SAP.

For analysis comparing proportion of treatment-emergent abnormalities between treatment groups for laboratory analytes, vital signs, weight, MRI scans, skin and eye examinations, and ECGs, only patients who have both a baseline observation and a postbaseline observation will be included in the analysis for each analyte or parameter, respectively.

Suicide-related thoughts and behaviors, based on the C-SSRS, will be listed by patient and visit. Only patients that show suicidal ideation/behavior will be displayed (that is, if a patient's answers are all "no" for the C-SSRS, then that patient will not be displayed). However, if a patient reported any ideation or behavior at any time point, then all their ideation and behavior will be displayed, even if not positive.

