5.1. Summary of Study Design

[figure not shown]
Study I8D-MC-AZET (AZET) is an international, multicenter, randomized, parallel-group, 78 week double-blind (DB), placebo-controlled study of 2 fixed dose levels of LY3314814 (20 mg or 50 mg) in patients with mild AD dementia and abnormal levels of amyloid, followed by a 78 week Delayed-Start period.

Study AZET is the second Phase 3 study that was initiated after a safety interim analysis of an ongoing Phase 2/3 study [I8D-MC-AZES] in an early AD (mild cognitive impairment [MCI] due to AD and mild AD dementia) population. Study AZET will only enroll patients with mild AD. This study is 18 months (78 weeks) in duration for the primary outcome. Studies of this duration, in mild AD dementia patients, are believed to be of sufficient length to detect a difference from the placebo decline rate (Liu-Seifert et al. 2015).

The purpose of the Delayed-Start period of AZET is to assess whether LY3314814 has an effect independent of acute symptomatic effects otherwise consistent with disease modification or slowing of disease progression. In other words, the objective of the Delayed-Start period is to determine if the patients originally randomized to receive placebo and switched to LY3314814 at the start of the Delayed-Start period could achieve the same outcome after receiving 6 months of active therapy (at Week 104) as patients originally randomized to receive LY3314814 in the double-blind period. This objective will be evaluated using all available data through Week 104 by the time of database lock of the Placebo-Controlled period. After the study was stopped for futility, all ongoing patients were asked to come in for a futility-based discontinuation visit. Patients at this visit followed the schedule of events for an early discontinuation visit.

Figure AZET.SAP.1 illustrates the study design.

Figure AZET.SAP.1 Illustration of Study Design for Clinical Protocol I8D-MC-AZET.

Abbreviations: LY=LY3314814

^{*}At Visit 2, patients randomized to placebo in the Placebo-Controlled period will also be randomly assigned to a Delayed-Start treatment group to begin at Week 78. This will be achieved by randomizing patients to one of four

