6.13.4. Clinical Laboratory Evaluations

Laboratory measures will be analyzed both as continuous data (change from baseline) and categorical or ordinal data (proportions of treatment-emergent abnormalities).

If there are multiple records of laboratory measurements at a baseline or post-baseline visit, the latest record will be used.

Summaries and analyses of continuous data (change from baseline) will use both conventional and International System of Units (SI units).

For the Placebo-controlled period, change from baseline to post-baseline visits will be compared between treatment groups using an MMRM model. For each lab analyte, the rank-transformation will be applied to the change from baseline for all subjects and all visits prior to analysis. Similarly, an independent rank transformation will be applied to the baseline values prior to analysis. The model for the fixed effects will include terms for: baseline, treatment, visit, and the treatment-by-visit interaction. This analysis will be done separately for each lab analyte. For the Delayed-Start period, mean change from baseline to post-baseline visits will be summarized.

For the Placebo-Controlled period, treatment differences in the proportions of subjects with treatment-emergent high or treatment emergent low or treatment-emergent abnormal laboratory values at (1) anytime and (2) each post-baseline visit will be assessed using Fisher's Exact Test. Treatment-emergent high or low abnormalities will be calculated using SI units. For each lab analyte, only those subjects who were low or normal at baseline and have at least one post-baseline measurement will be included in the denominator when calculating the proportion of subjects with treatment-emergent high values. Similarly, only subjects who were high or normal at baseline and have at least one post-baseline measurement will be included in the denominator when calculating the proportion of subjects with treatment-emergent low values. In addition, treatment differences in the proportion of subjects who were normal at baseline and change to abnormal high or abnormal low values at any post-baseline visit will be summarized. For the Delayed-Start period, the proportions will be summarized.

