6.13.5. Vital Signs and Other Physical Findings

Vital sign measurements and weight will be analyzed using continuous data (change from baseline) and categorical data (proportion of potentially clinically significant changes).

If there are multiple records of vital sign or weight measurements at baseline or a postbaseline visit, the last record will be used. Summary statistics will be presented for observed values at baseline and for change from baseline results at each scheduled postbaseline visit. Systolic and diastolic blood pressure and pulse (collected in sitting position), orthostatic diastolic and orthostatic systolic blood pressures and orthostatic pulse (measurement after 5 minutes in the supine position minus that after 2 and 5 minutes in the standing position), temperature, and weight by treatment group for all subjects in the safety population will be summarized.

With the large number of visits at which vital signs are scheduled to be measured, the MMRM model is not suitable for the change from baseline comparison of treatments. In the Placebo-Controlled period change from baseline to each post-baseline visit at which vital signs are taken will be assessed using an ANCOVA model with treatment and as independent factors and baseline value and age as covariates in the model. This analysis will be done separately for each vital sign parameter and weight. In the Delayed-Start period, these changes will be summarized.

The incidence of treatment-emergent abnormal high or low vital signs and weight will be presented by treatment group and visit. Treatment-emergent vital sign evaluations are defined for evaluations collected after the initiation of study medication. Abnormal criteria for postbaseline vital signs and weight are presented in Appendix 5. Any vital sign or weight meeting the criteria will be considered abnormal. In the Placebo-Controlled period, treatment differences in the proportion of subjects with treatment-emergent abnormal high or low vital signs and weight will be assessed between treatment groups using Fisher's Exact test at (1) any time and (2) by post-baseline visit.

For each vital sign at each post-baseline visit, only subjects who had a baseline result and had a nonmissing result at that post-baseline visit will be included in the denominator when computing the proportion of subjects with treatment-emergent high, low, or abnormal values.

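### SAP 6.13.4 gives one denominator rule for both any-time and by-visit laboratory abnormality tables; applied as written, it understates the by-visit percentages, increasingly at later visits

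*SAP*

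**What the plan says.** SAP 6.13.4 (Clinical Laboratory Evaluations) plans two sets of comparisons for the Placebo-Controlled period: treatment-emergent "laboratory values at (1) anytime and (2) each post-baseline visit will be assessed using Fisher's Exact Test".

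The denominators follow within the same paragraph. For treatment-emergent high values, "only those subjects who were low or normal at baseline and have at least one post-baseline measurement will be included in the denominator". For treatment-emergent low values, "only subjects who were high or normal at baseline and have at least one post-baseline measurement will be included in the denominator". Neither sentence is confined to the any-time comparison, and neither asks for a result at the visit being tabulated. The section gives no other denominator for these proportions.

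SAP 6.13.5 plans the same pair of comparisons for vital signs and weight, and there the by-visit rule is explicit: "only subjects who had a baseline result and had a nonmissing result at that post-baseline visit will be included in the denominator".

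Protocol 10.3.4 does not settle the matter for laboratory data. It says that "only patients who have both a baseline observation and a postbaseline observation will be included in the analysis for each analyte or parameter", with no visit-specific condition.

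**The concern.** A patient whose only post-baseline sample is from Week 4 meets the stated rule. Applied to the Week 78 table, the rule keeps that patient in the denominator, although the patient has no Week 78 result and cannot enter the numerator. The missing result is in effect scored as normal.

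The number of such patients grows with each visit. An abnormality rate that is constant among those tested would therefore appear to fall with longer dosing. If more patients leave one arm than the other, that arm's late-visit rates shrink more, and it looks safer without being so.

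This matters for a drug whose protocol lists raised liver enzymes as a potential risk (Protocol 3.3) and liver toxicity as an event of special interest (Protocol 9.4.9.1). Laboratory safety is still reported after the futility stop.

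**Working it through.** **Inputs**

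- Dropout, Protocol synopsis: "If there is an assumed 25% discontinuation rate, approximately 1424 patients will complete the Placebo-Controlled period".
- Total size, Protocol 10.1: "This equates to a total randomized sample size of 1899", which is 633 per group.
- Laboratory visits after baseline, Protocol Table 2.2: Weeks 4, 7, 13, 26, 39, 52, 65 and 78.

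**The plan's own figure.** 1899 × 0.75 = 1424.25, so the stated 1424 completers are reproduced.

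**Formula.** Let m be the number of baseline-eligible patients tested at a visit, M the number of baseline-eligible patients ever tested after baseline, and p the rate among those tested. The rule as written reports p × m / M. The relative understatement is 1 − m/M.

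**Planned dropout.** Assume that the 25% is lost evenly over 78 weeks, so retention at week w is 1 − 0.25 × w/78. Take patients present at Week 4, the first scheduled post-baseline sample, as ever tested: 1 − 0.25 × 4/78 = 0.987. The last column assumes a constant true rate of 5%.

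| Visit | Retained | m/M | Understated by | A constant 5% is shown as |
|---|---|---|---|---|
| Week 26 | 0.917 | 0.917/0.987 = 0.93 | 7% | 4.6% |
| Week 52 | 0.833 | 0.833/0.987 = 0.84 | 16% | 4.2% |
| Week 78 | 0.750 | 0.750/0.987 = 0.76 | 24% | 3.8% |

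Analytes first retested at Week 26 (lipids, HbA1c and thyroid tests, Protocol Appendix 2) are less affected: 0.750/0.917 = 0.82 at Week 78.

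**Fisher test, equal attrition.** For simplicity, let all 633 per arm be baseline-eligible and ever tested, with 475 tested at Week 78 (633 × 0.75). Assume true rates of 10% on drug and 5% on placebo.

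- Visit-specific denominator: 48/475 = 10.1% versus 24/475 = 5.1%, p = 0.0045.
- As written: 48/633 = 7.6% versus 24/633 = 3.8%, p = 0.0049.

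**Fisher test, unequal attrition.** Assume a true rate of 10% in both arms. The attrition splits are also assumed.

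- 70% versus 80% tested: 44/443 = 9.9% versus 51/506 = 10.1% (p = 1.0) becomes 44/633 = 7.0% versus 51/633 = 8.1% (p = 0.52).
- 50% versus 75% tested: 32/316 = 10.1% versus 48/475 = 10.1% (p = 1.0) becomes 32/633 = 5.1% versus 48/633 = 7.6% (p = 0.08).

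**Early stop, illustration only.** Suppose potential follow-up is uniform on 0 to T weeks, a share r of patients could reach Week 78 (so T = 78/(1 − r)), and dropout is exponential at 25% per 78 weeks. Then m/M at Week 78 is 0.75r / [(1 − 4/T) × 0.75^(4/78)].

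- r = 0.20: 0.150/0.945 = 0.16
- r = 0.35: 0.2625/0.953 = 0.28
- r = 0.50: 0.375/0.960 = 0.39

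Neither r nor the accrual pattern is in the documents.

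**The case against.** **The rule may be meant only for the any-time table.** Its wording is natural for that table, and 6.13.5 writes out only the by-visit rule although it too plans both comparisons. The two sections could be mirror-image incomplete drafting, and a programmer might use a visit-specific denominator anyway. This stands in part. The sections cover different measurements, so they are inconsistent rather than contradictory. Still, the laboratory rule is stated without limit, directly after both comparisons are named, and nothing in the SAP tells the programmer to depart from it.

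**Other analyses give cover.** The any-time comparison, the any-time ALT and bilirubin criteria and the Hy's Law analysis are untouched. The by-visit repeated-measures model on ranked change uses observed data and would help to show whether an apparent decline is real. SAP 6.1 also says that no test will be interpreted as significant. All of this stands and limits the consequence, but it does not make the by-visit percentages right.

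**The between-arm effect may be small.** Loss of late visits through the trial stop is administrative and should be balanced by randomization. This also stands: the documents give no arm-specific dropout, so the unequal cases above show only what could happen.

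**A reader might infer that late-visit rates are understated by well over half.** The 0.16 to 0.39 range would mean 61% to 84% at Week 78. The documents do not support stating this as a finding. SAP 5.1 reports that "After the study was stopped for futility, all ongoing patients were asked to come in for a futility-based discontinuation visit", but no section gives accrual dates or numbers tested by visit, or says how results from that visit map to scheduled weeks. SAP 6.12.2.1 says that very few patients had Delayed-Start exposure, which sits poorly with the 35% and 50% cases.

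**Conclusion.** The point holds for the by-visit laboratory tables only. Applied as written, the rule counts baseline-eligible patients without a result at the visit as not abnormal. The denominator is not every patient ever tested, because the baseline-status restriction still applies.

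The size that the documents can anchor is about 16% relative understatement at Week 52 and 24% at Week 78. It rests on the planned 25% dropout, an even spread over time, and Week 4 as the first post-baseline sample. The earliest visits are hardly affected. The early stop would make the understatement larger, by an amount that the documents do not fix.

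With equal attrition the damage is to the percentages and the apparent trend over visits, not to the tests. A claim that the drug arm will look safer would need higher attrition on drug, which the documents do not report. Nor do they show the same error for ECGs: SAP 6.13.6 states no by-visit denominator, which is missing detail rather than a wrong rule. The correction should be made before the by-visit tables are produced.

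**What to change.** In SAP 6.13.4, confine the present rule to the any-time comparison. For each by-visit comparison, define the denominator as:

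- patients low or normal at baseline (for treatment-emergent high) or high or normal at baseline (for treatment-emergent low), and
- with a nonmissing result for that analyte at that visit.

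This matches the vital-sign rule in SAP 6.13.5. Print the number tested at each visit beside the percentage, so that the shrinking late-visit base is visible.

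The cost is one sentence in the SAP and one filter in the by-visit table programs. No new data are needed, and the any-time results do not change.

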- [25] Screening magnetic resonance imaging (MRI) shows evidence of >5 microhemorrhages; prior macrohemorrhage (>1 cm³); ≥4 infarcts, evidence of cerebral contusion, encephalomalacia, space-occupying lesion with mass-effect and edema

Note: Cortical superficial siderosis is not an exclusion.

- [26] Uncontrolled hypertension, that is, supine systolic blood pressure >165 mmHg or diastolic blood pressure >95 mmHg. If an initial blood pressure reading is higher than this, an additional attempt (at this visit or on another day) could be used before excluding a patient for uncontrolled hypertension.
- [27] Known positive serologic findings for human immunodeficiency virus (HIV) antibodies. Local laws and regulations may apply to whether testing is required.
- [28] Patients with past history (suspected or confirmed) of Hepatitis B should have HBsAg testing at screening and are excluded if HBsAg is positive.
  - Patients with past history (suspected or confirmed) of Hepatitis C (resolved >6 months prior to enrollment) should have hepatitis C virus (HCV) ribonucleic acid (RNA) polymerase chain reaction (PCR) testing at screening and are excluded if HCV RNA PCR is positive.
  - Patients in high-prevalence regions may be required to have screening serology.
- [29] Any clinically important abnormality at screening, as determined by investigator, in physical or neurological examination, vital sign, ECG, or clinical laboratory test results that could be detrimental to the patient or could compromise the study
- [30] Calculated creatinine clearance <30 mL/min (Cockcroft-Gault formula; Cockcroft and Gault 1976) at screening
- [31] Alanine aminotransferase (ALT)  $\geq$ 2x the upper limit of normal (ULN) of the performing laboratory, aspartate aminotransferase (AST)  $\geq$ 2x ULN, total bilirubin  $\geq$ 1.5x ULN, or alkaline phosphatase (ALP)  $\geq$ 1.5x ULN at screening

NOTE: Patients with total bilirubin  $\ge$ 1.5 x ULN are not excluded if they meet all of the following criteria for Gilbert syndrome:

- 1. Bilirubin is predominantly indirect (unconjugated) at screening (direct bilirubin within normal limits)
- 2. Absence of liver disease
- 3. ALT, AST, and ALP ≤1x ULN at screening
- 4. Hemoglobin not significantly decreased at screening

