### 9.4.9.1. Adverse Events of Special Interest

Adverse events of special interest will include:

- Adverse eye effects including retina (Section 9.4.7)
- Adverse skin effects including rash (Section 9.4.9.3) and hypopigmentation (Section 9.4.8)
- Peripheral nervous system, central nervous system and muscle effects
- Liver toxicity (Section 9.4.9 and Section 8.1.1)
- Cardiovascular (CV)-type events (including, but not limited to, orthostatic hypotension and QT prolongation) (Section 9.4.9.2)

The topics listed above, as well as new topics which may be subsequently determined by the Sponsor, will be subject to enhanced surveillance activities. Additionally, the topics above will be analyzed for presentation in the Clinical Study Report in accordance with the Statistical Analysis Plan (SAP).

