A second categorical analysis will be conducted on laboratory analytes. This analysis is considered a PCS analysis and will use limits typically wider than the first categorical analysis. Abnormal criteria for these treatment-emergent PCS changes are presented in **Error! Reference source not found.**

For urinalysis parameters, baseline to post-baseline shifts will be summarized at each visit. For the Placebo-Controlled period, likelihood ratio chi-square tests will be used to compare increase, no change and decrease shifts in urinalysis parameters between treatment groups at each visit.

For all laboratory analytes, frequencies of subjects with notable changes (that is, increases or decreases of a prespecified amount unique to each analyte) from baseline to each postbaseline visit were also summarized for all subjects and stratified by low, normal, or high at baseline.

The proportion of subjects with treatment-emergent clinically significant changes from a low value or normal value at all baseline at any time in ALT and total bilirubin will be summarized by treatment group. Clinically significant changes of interest are: $ALT \ge 3$ x upper limit of

normal (ULN) and total bilirubin ≥ 2 x ULN, AST ≥ 3 x ULN, ALT ≥ 5 x ULN, ALT ≥ 10 x ULN, and total bilirubin ≥ 2 x ULN. Additionally, Hy's Law analysis will be conducted by comparing treatment groups with regard to the proportion of patients with (ALT ≥ 3 x ULN OR AST ≥ 3 x ULN) AND total bilirubin ≥ 2 x ULN. Comparisons between treatment groups will be carried out using Fisher's Exact test in the Placebo-Controlled period. When criteria are met for hepatic evaluation and completion of the hepatic safety case report form (CRF), investigators are required to answer a list of questions pertaining to the patient's history, relevant pre-existing medical conditions, and other possible causes of liver injury. A listing of the information collected on the hepatic-safety CRF will be generated.

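### The graded liver table in SAP 6.13.4 leaves out patients whose liver values were already raised at baseline, and no other by-arm table counts ALT ≥5x or ≥10x ULN in all patients

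*SAP*

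**What the plan says.** SAP 6.13.4 (Clinical Laboratory Evaluations) plans a by-treatment summary of treatment-emergent, clinically significant liver changes. It covers "changes from a low value or normal value at all baseline at any time in ALT and total bilirubin". The changes listed are ALT ≥3x together with total bilirubin ≥2x ULN, AST ≥3x ULN, and then "ALT ≥ 5 x ULN, ALT ≥ 10 x ULN, and total bilirubin ≥ 2 x ULN". Arms are compared with Fisher's exact test in the Placebo-Controlled period.

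The first categorical laboratory analysis in the same section uses a similar condition for high values and applies it one analyte at a time: "For each lab analyte, only those subjects who were low or normal at baseline and have at least one post-baseline measurement" enter the denominator.

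Protocol 6.2, criterion [31], sets the entry limit for ALT at "2x the upper limit of normal (ULN) of the performing laboratory" and the same multiple for AST. Total bilirubin is limited at 1.5x ULN, but patients above that "are not excluded if they meet all of the following criteria for Gilbert syndrome".

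Protocol 10.3.4 asks only for a baseline and a post-baseline observation when proportions of treatment-emergent laboratory abnormalities are compared. It sets no normal-at-baseline condition.

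**The concern.** The entry rule and the counting rule do not match. Patients with mildly raised liver enzymes are admitted by design, and the table that grades liver rises then leaves them out. They start closest to the thresholds, so they need the smallest further rise to cross one.

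The table has a specific job. The protocol lists "Liver toxicity (Section 9.4.9 and Section 8.1.1") among its adverse events of special interest, and Protocol 3.3 names elevated liver enzymes as a potential risk. After the futility stop, the SAP treats efficacy results as hypothesis-generating and summarizes only safety data from the Delayed-Start period, so the safety tables carry much of the remaining information. Rises to 5x or 10x ULN are likely to be few, and the loss of one or two from the graded count could change how it reads.

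**Working it through.** The documents give no figure on this point: no prevalence of raised baseline values and no expected count at 5x or 10x ULN. The main check is therefore of the text, followed by an illustration of size.

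**1. Who can enter but not be counted.** A patient with ALT of 1.5x ULN at screening is below the 2x limit in criterion [31] and can be randomized. That value is not low or normal. If ALT reaches 6x ULN on treatment, the patient meets the ≥5x level but fails the baseline condition in SAP 6.13.4.

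**2. Whether another planned output supplies the count.**

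| Planned output | Baseline condition | What it gives for this patient |
|---|---|---|
| High/low categorical analysis (SAP 6.13.4) | low or normal for treatment-emergent high | not counted as high |
| Potentially clinically significant (PCS) analysis (SAP 6.13.4, Appendix 3) | called treatment-emergent, not defined | ALT or AST ≥3x, bilirubin ≥1.5x ULN; no 5x or 10x level |
| Notable-change summary (SAP 6.13.4) | all subjects, split by baseline status | amounts not given |
| Hy's Law (SAP 6.13.4) | none stated | needs bilirubin ≥2x as well as ALT or AST ≥3x |
| Hepatic CRF listing (SAP 6.13.4) | none stated | a listing, not a comparison of arms |

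None gives ALT ≥5x or ≥10x by arm in all patients.

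**3. What the condition leaves open.** SAP 6.1.1 defines baseline as the last non-missing value from Visits 1 and 2, and laboratory tests are scheduled at both. The liver sentence instead refers to all baseline. If that means every baseline value, one raised result at either visit removes the patient. The sentence names ALT and bilirubin but not AST, although AST ≥3x is on the list. It does not state the denominator.

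**4. Size, for illustration.** The arm size is from SAP 5.2: 554/(1 − 0.25 × 0.50) = 633.1, which agrees with the stated 633, and 3 × 633 = 1899. Let k be the patients per arm with raised baseline ALT and R their risk of reaching ALT ≥5x relative to the rest. The share of such events left uncounted is kR / [(633 − k) + kR]. The prevalence and R are assumptions.

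| Assumed prevalence | k per arm | Of 1899 | R = 1 | R = 3 | R = 5 |
|---|---|---|---|---|---|
| 2% | 13 | 38 | 2.1% | 5.9% | 9.5% |
| 5% | 32 | 95 | 5.1% | 13.8% | 21.0% |
| 10% | 63 | 190 | 10.0% | 24.9% | 35.6% |

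**5. Effect on the proportion.** Assume a 0.5% event rate in patients normal at baseline, and that excluded patients leave both numerator and denominator. The table then shows 0.50% whatever R is. The all-patient proportion at R = 1 is also 0.50%. At 10% prevalence and R = 5 it is (570 × 0.005 + 63 × 0.025)/633 = 4.425/633 = 0.70%. If excluded patients stay in the denominator without being able to count as events, the table shows 570 × 0.005/633 = 0.45% at that prevalence, too low even at R = 1.

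**The case against.** The strongest reply is that the condition is a recognizable definition of treatment emergence, consistent with the first categorical analysis, and that these patients are not lost from view. Much of this stands.

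- The PCS paragraph states no normal-baseline condition. A patient admitted at 1.5x ULN is below its 3x limit at screening and meets it on reaching 6x. Its bilirubin row, at 1.5x ULN, is a lower bar than 2x.
- The notable-change summary includes all subjects and shows those high at baseline as their own stratum.
- Hepatic follow-up under Protocol 9.4.9 is triggered by multiples of ULN whatever the baseline. Liver adverse events, including worsened ones, are compared by arm through the hepatic cluster in SAP 6.13.3.
- Criterion [29] lets the investigator exclude clinically important laboratory abnormalities, which narrows the affected group without removing it.

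So detection is largely covered. What these outputs do not supply is the 5x and 10x grading by arm in all patients.

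Three stronger readings are tempting, and the documents do not support them:

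- **Raised ALT also removes patients from the bilirubin ≥2x row.** This needs ALT and bilirubin to be one joint condition. The sentence can be read that way, but the section's own convention is analyte by analyte. On that reading, only raised baseline bilirubin affects the bilirubin row.
- **The liver signal is understated.** If excluded patients leave both numerator and denominator, the proportion is too low only if they cross thresholds more often than the rest. Being closer to the threshold makes this plausible, but the documents give no such rate.
- **The comparison between arms is biased.** The exclusion uses pre-treatment status and applies equally to all arms, so nothing in the documents shows bias in favour of one arm.

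**Conclusion.** The point holds as a gap in the graded count. On either reading of the baseline condition, a patient with ALT between 1x and 2x ULN at baseline cannot be counted at ALT ≥5x or ≥10x, and no other by-arm table gives those counts in all patients. Patients admitted with raised bilirubin are likewise left out of the bilirubin ≥2x row, although the PCS row at 1.5x gives partial cover.

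The size is unknown. About 38 to 190 of 1899 patients would be affected if 2% to 10% had raised ALT at baseline. The uncounted share of ALT ≥5x events would run from about 2% (2% prevalence, equal risk) to about 36% (10% prevalence, fivefold risk). These ranges rest on assumed prevalences and risks and on the planned randomized number. They show scale and are not estimates for this trial. Whether the reported proportion is too low depends on relative risk and on the denominator, neither of which is stated for this table.

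This is an inexpensive improvement to the reporting of an event of special interest. It does not show that liver cases would go undetected.

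**What to change.** In SAP 6.13.4:

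1. For each threshold row, count all treated patients with at least one post-baseline value whose own baseline for that analyte was below the row's threshold, and use the same patients as the denominator.
2. Show the normal-at-baseline and raised-at-baseline subsets beside the total. The first keeps the display now planned.
3. State that the baseline condition is applied analyte by analyte, including for AST, and give a separate rule for the combined ALT-and-bilirubin row.
4. Replace the reference to all baseline with a defined term: either the last value before treatment, as in SAP 6.1.1, or every value at Visits 1 and 2.

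The cost is a few sentences of SAP text, a changed denominator and two extra sets of columns, using data already collected. Trial conduct is not affected. The total count will be slightly noisier, because some patients start nearer a threshold and may cross it through ordinary variation. The split by baseline status lets the reader see this.
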